### 5.1.2 Other Modality(ies) or Procedures

*Patients' tears will be collected through contact lenses (4 days worth from both eyes of each patient), which will be stored in unused contact lens containers daily and subsequently collected during routine 1 week follow-up appointments with Nuclear Medicine. The lenses will be analyzed for radioactive iodine levels. Routine post-radioiodine imaging (single-photon emission computed tomography and/or whole body scintigraphy) will be obtained to assess for radioactivity in the nasolacrimal or intranasal region.*

## **6. STATISTICAL CONSIDERATIONS**

*Radioactive iodine levels from the right contact lenses of patients will be compared to that of the left contact lenses that did not have exposure to artificial tears. The data gathered will be analyzed by the statistics personnel in the department of Ophthalmology.*

*In more detail: the area under the curve (AUC) of all four days for each patient was calculated as the sum of the four trapezoid areas under the I-131 exposure values. To meet the normality assumption, I-131 activities and AUCs were logarithmically transformed to obtain geometric mean I-131 activities of each day and geometric mean AUCs. The Shapiro-Wilk test was used to evaluate the normal assumption for logarithmically transformed AUCs (log-AUCs). The 95% confidence intervals (CI) of the AUCs were constructed for the right experimental eyes and left control eyes, assuming normality for log-AUCs, which were compared between the two groups using paired t-tests. Statistical analyses were conducted using R version 4.1.2 (R Project for Statistical Computing, [www.r-project.org](http://www.r-project.org)). Two sided  $p < 0.05$  was considered statistically significant.*

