## **1. OBJECTIVES**

### **1.1 Primary Objectives**

1.1.1 *To assess whether use of preservative free artificial tears following radioactive iodine administration will lower the level of radioactive iodine in the tears of patients treated with radioactive iodine for thyroid carcinoma.*

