## **5. TREATMENT AND/OR IMAGING PLAN**

### **5.1 Agent Administration**

*Artificial tears are the study agent of interest and bear minimal risks and side effects. The regimen for self-administration of artificial tears is as follows: on Day 1, patients will self-administer artificial tears every 15 minutes for 2 hours followed by every 30 minutes for 4 hours. On Day 2, patients will self-administer artificial tears every 1 hour for 12 hours. On Day 3, patients will self-administer artificial tears four times that day. On Day 4, patients will self-administer tears twice that day. Patients will be instructed to wear their contact lenses throughout their waking hours. The rationale for this proposed regimen is to dilute the radioactive iodine from the tear ducts with frequent administration of artificial tears. Zettinig et al showed that radioiodine levels are highest in tears on the first day and significantly decrease over 4-5 days, which serves as the underlying rationale for having patients self-administer artificial tears for four days.*

*Routine whole body scintigraphy (WBS) and/or single photon emission computed tomography (SPECT-CT) will be obtained around 1 week post-radioiodine as part of the routine care patients receive after having radioiodine administration for treatment of thyroid cancer. No adjustments will be made to this routine imaging that patients receive. We will analyze the routine images for localization of radioiodine in the intranasal and nasolacrimal duct regions.*

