#### **5.1.1 Primary and Secondary Endpoint**

*The primary endpoint will be to assess for the development of nasolacrimal duct obstruction over two years in 8 month intervals. Every 8 months, each patient will be assessed in the ophthalmology clinic for nasolacrimal duct dysfunction via tear duct irrigation. The secondary endpoint is the level of radioactive iodine measured in the tears of patients collected via their contact lenses. Patients will be asked to store their daily contact lenses in sterile container for subsequent radioactive iodine level analysis via a well counter in the Nuclear Medicine department. These contact lenses will be collected at their 1 week routine appointment with Nuclear Medicine.*

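### Does summing four trapezoids from four daily lens values leave the tear-iodine AUC undefined?

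*Combined protocol and SAP*

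**What the plan says.** Section 6 (Statistical Considerations) takes as its summary measure "the area under the curve (AUC) of all four days for each patient". The rule for computing it is that it "was calculated as the sum of the four trapezoid areas under the I-131 exposure values". The AUCs are log-transformed, given 95% confidence intervals separately for the right (treated) and left (control) eyes, and compared by paired t-test at two-sided 0.05. Section 6 also plans "geometric mean I-131 activities of each day and geometric mean AUCs".

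The data behind the AUC are described in section 5.1.2: lenses stored daily, "4 days worth from both eyes of each patient". That gives one value per eye per day for Days 1 to 4. No section gives a value at time zero or on Day 5, an extrapolation rule, or the clock time assigned to each lens.

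Section 5.1 expects that "radioiodine levels are highest in tears on the first day and significantly decrease over 4-5 days". Its drop schedule is heaviest at the start: "on Day 1, patients will self-administer artificial tears every 15 minutes for 2 hours followed by every 30 minutes for 4 hours", falling to two administrations on Day 4.

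**The concern.** The number of trapezoids does not match the number of measurements, so a reader cannot reproduce the AUC from the text alone. The choice of fifth point decides how much weight Day 1 receives, and Day 1 is where the protocol expects the highest activity and schedules the most drops.

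The AUC also feeds the only between-eye test that is spelled out. Section 1.1 makes tear iodine the primary objective, asking whether artificial tears "will lower the level of radioactive iodine in the tears of patients", although section 5.1.1 ranks it lower: "The secondary endpoint is the level of radioactive iodine measured in the tears of patients collected via their contact lenses". With 5 patients, an analyst who left the fifth point open until the data were in could, in principle, choose among several AUCs. The wording also refers to one AUC per patient, whereas a paired test needs one per eye.

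**Working it through.** **Count.** k points bound k − 1 trapezoids, so four daily values bound 4 − 1 = 3. The plan's figure of four needs five points. It cannot be reproduced from the lens values alone, but it can be with one anchor value.

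**Which anchor fits the text.** Section 6 combines a four-day span with four trapezoids, that is, four one-day intervals. With activity zero at administration and D1 to D4 at the four following days:

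AUC = (0 + D1)/2 + (D1 + D2)/2 + (D2 + D3)/2 + (D3 + D4)/2 = D1 + D2 + D3 + 0.5 × D4.

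Three trapezoids would require the word four to be a slip. A zero at Day 5 leaves out the interval before the Day 1 value and assumes that activity has gone, whereas section 5.1 says only that it falls over 4 to 5 days.

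**Weights.** Control-eye activities of 100, 50, 25 and 12.5 are assumed.

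| Reading | Weights, Days 1–4 | AUC | Day 1 share |
|---|---|---|---|
| Zero at administration | 1, 1, 1, 0.5 | 100 + 50 + 25 + 6.25 = 181.25 | 55% |
| Three trapezoids | 0.5, 1, 1, 0.5 | 50 + 50 + 25 + 6.25 = 131.25 | 38% |
| Zero at Day 5 | 0.5, 1, 1, 1 | 50 + 50 + 25 + 12.5 = 137.5 | 36% |
| Plain sum | 1, 1, 1, 1 | 187.5 | 53% |

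**Is an effect that varies by day plausible?** Scheduled drops are about 120/15 + 240/30 = 8 + 8 = 16 on Day 1, then 12, 4 and 2. So yes, on the protocol's own dilution rationale.

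**Right/left AUC ratio.** One case in full: daily ratios 0.4, 0.5, 0.8, 0.9 with control activity halving daily give right-eye values of 40, 25, 20 and 11.25.

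- Zero start: (40 + 25 + 20 + 5.625)/181.25 = 0.500.
- Three trapezoids: (20 + 25 + 20 + 5.625)/131.25 = 0.538.
- Zero at Day 5: (20 + 25 + 20 + 11.25)/137.5 = 0.555.
- Plain sum: 96.25/187.5 = 0.513.

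The same calculation for other assumed inputs:

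| Daily ratios | Control factor per day | Zero start | Three trapezoids | Zero at Day 5 | Plain sum |
|---|---|---|---|---|---|
| 0.4, 0.5, 0.8, 0.9 | 0.3 | 0.452 | 0.481 | 0.487 | 0.456 |
| | 0.5 | 0.500 | 0.538 | 0.555 | 0.513 |
| | 0.7 | 0.549 | 0.589 | 0.615 | 0.573 |
| 0.2, 0.4, 0.8, 1.0 | 0.3 | 0.289 | 0.338 | 0.348 | 0.296 |
| | 0.5 | 0.366 | 0.429 | 0.455 | 0.387 |
| | 0.7 | 0.442 | 0.507 | 0.549 | 0.480 |

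The rival readings lie above zero start by 0.481 − 0.452 = 0.029 at least and 0.549 − 0.442 = 0.107 at most. The plain sum lies above it by 0.456 − 0.452 = 0.004 to 0.480 − 0.442 = 0.038. With a constant daily ratio, all four columns are identical.

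**Effect on the test (illustrative only).** Paired t-tests on log-AUC were simulated with 5 pairs, control activity halving daily, the two sets of daily ratios above and independent lens-level log SD of 0.5 to 1.0. The p < 0.05 verdict differed between zero start and three trapezoids in 5–12% of trials, between zero start and zero at Day 5 in 6–15%, and between zero start and the plain sum in 1–5%. These figures move a good deal with the assumptions. At log SD 0.3 the two effect profiles above give about 1% or less, but a milder profile (0.5, 0.7, 0.9, 1.0) gives about 11% for three trapezoids and 12% for zero at Day 5. At log SD 1.0, noise correlated 0.8 within an eye cuts one figure for three trapezoids from 8.1% to 2.6%.

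**Per patient or per eye.** Section 6 builds separate intervals for right and left eyes and then pairs them, so one AUC per eye is what is computed.

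**The case for a change.** The strongest case for a change is that the AUC carries the only specified test, the anchor is unstated, and the readings differ most where the protocol expects the signal. Two of the three trapezoidal readings halve the weight of Day 1. The three do not exhaust the choices either. With control activity halving daily and ratios of 0.5, 0.7, 0.9 and 1.0, zero start gives 0.628, while other fifth points run from 0.531 (log-linear back-extrapolation) to 0.708 (one non-zero start shared by both eyes). A shared non-zero start shifts the ratio even when the effect is constant, from 0.700 to 0.765. Naming the anchor would take one sentence and no new data. The daily geometric means help a reader see the pattern, but no test of them is described.

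What stands is that the fifth point is missing and that the result would depend on it if an unusual one were used. What does not stand is that the analysis is therefore unsound or undetermined. The larger shifts need either a correction to the stated number of trapezoids or an anchor that nothing in the text suggests. A zero at administration needs neither, and it is the obvious starting value because no radioiodine has yet reached the tears. Replacing the AUC with a plain sum is a preference and has not been shown to be better. As the analysis is written in the past tense, it would also risk a post hoc change of outcome.

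**Conclusion.** No change follows. The plan omits a detail that an analyst fills in one sensible way: zero activity at administration, with AUC per eye = D1 + D2 + D3 + 0.5 × D4. That rule uses every lens, keeps full weight on Day 1, halves only Day 4 (the day expected to be lowest) and applies equally to both eyes, so the paired log-AUC comparison is valid.

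If one of the two main rival readings had been used, the right/left ratio would be higher by about 0.03 to 0.11 in the assumed cases. It would still be well below 1 in each of them, and unchanged if the tear effect is constant across days. Against a plain four-day sum, the zero-start AUC differs by at most 0.038.

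The mismatch in the count follows from the documents alone and is certain. Its size rests on assumed activities, daily ratios and variances, so the simulated verdict differences show only that the choice can matter at n = 5. They do not show how much it matters in this trial.

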## **7. ADVERSE EVENTS: LIST AND REPORTING REQUIREMENTS**

*Preservative-free artificial tears have rare side effects. Because they are preservative free, there is minimal harm to the cornea. Possible side effects include watery eyes, possible allergic reaction, eye irritation not present before use of the artificial tears, or possible blurry vision. Persistent irritation of the eyes is an indication for stopping artificial tears. These side effects will likely end with discontinuation of the artificial tears and are unlikely to have long-term sequela.*

*There have been no studies conducted regarding the dose delay or dose reduction of artificial tears. It is possible that increasing the frequency of administration of artificial tears may increase the risk of developing the above possible side effects.*

## **8. STUDY OVERSIGHT AND DATA REPORTING / REGULATORY REQUIREMENTS**

*The Vanderbilt-Ingram Cancer Center (VICC) oversees patient safety and data monitoring for its investigator-initiated and NIH-NCI funded clinical trials through its Data and Safety Monitoring Committee (DSMC). The purpose of the DSMC is to ensure the efficient implementation and management of VICC Data and Safety Monitoring Plan (DSMP). The Committee maintains authority to intervene in the conduct of studies as necessary to ensure clinical research performed at VICC achieves the highest quality standards.*

*The VICC DSMC meets on a quarterly basis and ad hoc to discuss data and safety monitoring of clinical trials and to oversee the VICC DSMP. Internal audits for compliance with adverse event reporting, regulatory and study requirements, and data accuracy and completion are conducted according to the VICC DSMP according to study phase and risk. The committee reviews all serious adverse events (SAE) on Vanderbilt sponsored investigator-initiated studies on a quarterly basis and provides DSMC SAE review reports to the Vanderbilt IRB.*

